## **5.2 *Treatment compliance***

Trained medical personnel will administer IMC-A12 and cetuximab. Treatment compliance will be monitored by drug accountability (Section 5.5); IMC-A12 and cetuximab administration will also be recorded in the patient's medical record.

## **5.3 *Packaging and labeling***

### **5.3.1 IMC-A12**

Cixutumumab is an anti-IGF-IR recombinant human monoclonal antibody of the IgG1 class. Cixutumumab drug product (DP) is a sterile, preservative-free solution for infusion of cixutumumab formulated in an aqueous solution at a concentration of 5 mg/mL (250 mg/50 mL) or 10 mg/mL (500 mg/50 mL vial) or 15 mg/mL (750 mg/50 mL). The buffer contains 10mM sodium citrate, 100mM sodium chloride, 100mM glycine, and 0.01% polysorbate 80.

Cixutumumab DP is a clear or slightly opalescent and colorless or pale yellow liquid without visible particles. The pH is 6.5. The osmolality is 310 mmol/kg.

All excipients used for the manufacture of cixutumumab DP are of pharmacopoeial grade. No animal-derived components are used in the manufacture of cixutumumab DP excipients.

Cixutumumab DP is compatible with infusion containers composed of polyolefin, polyvinyl chloride (PVC), ethylene vinyl acetate (EVA) and evacuated glass (USP Type II or local equivalent). An infusion bag composed of polyolefin, polypropylene, and polyethylene prefilled with 0.9% Sodium Chloride Injection, such as AVIVA, may also be used. The following have been found to be compatible for cixutumumab DP infusion:

- A polyethylene-lined PVC infusion set with a 0.22  $\mu$  m downstream high-pressure, protein-sparing in-line filter made of polyethersulfone of 10 cm^2 surface area
- A PVC infusion set with a 0.2  $\mu$  m protein-sparing filter made of polyethersulfone of 4.2 cm^2 surface area
- A polyethylene-lined PVC infusion set with a 0.2  $\mu$  m protein-sparing in-line filter made of polyethersulfone of 10 cm^2 surface area
- A polyurethane infusion set with a 0.2  $\mu$  m protein-sparing in-line filter made of polyethersulfone of 10 cm^2 surface area
- A polybutadiene tubing with a 0.2 $\mu$ m protein-sparing in-line filter made of polysulfone of 9 cm^2 surface area

### 5.3.2 Cetuximab

Cetuximab for injection is supplied by ImClone Systems in single-use, 50 mL vials containing 2 mg/mL of product.

## **5.4 Storage and Preparation**

### **5.4.1 IMC-A12**

Storage: Storage conditions of the drug product are located in section 4.2.1 of the Investigator's Brochure for Cixutumumab.

PREPARED CIXUTUMUMAB DOSING SOLUTION FOR INFUSION: Chemical and physical in-use stability for the prepared cixutumumab dosing solution has been demonstrated for up to 24 hours below 25°C (77°F). However, it is recommended that the prepared dosing solution be used immediately in order to minimize the risk of microbial contamination. If not used immediately, the prepared cixutumumab dosing solution must be stored under refrigeration at 2°C to 8°C (36°F to 46°F) for a duration not to exceed 24 hours. If the prepared solution is held at room temperature (below 25°C (77°F)) it must be used within 4 hours. DO NOT FREEZE AND/OR SHAKE PREPARED CIXUTUMUMAB DOSING SOLUTION FOR INFUSION.

### **5.4.2 Cetuximab**

Cetuximab must be stored under refrigeration at 2°C to 8°C (36°F to 46°F). DO NOT FREEZE CETUXIMAB. Drug supplies must be kept in a secure, limited-access storage area under the recommended storage conditions. Once cetuximab is removed from the vial, the recommended maximum time at room temperature is 8 hours.

## **5.5 Accountability**

It is the responsibility of the investigator to ensure that a current record of investigational product disposition is maintained at each study site where investigational products are inventoried and disposed. Records or logs must comply with applicable regulations and guidelines, and should include:

- the amount received and placed in the storage area
- the amount currently in the storage area
- the label identification number or batch number
- the dates and initials of the person responsible for each investigational product inventory entry/movement
- the amount dispensed to each patient, including unique patient identifiers
- the amount transferred to another area for dispensing or storage
- non-study disposition (eg, lost, wasted, broken)
- the amount returned to ImClone Systems or a designee
- the amount destroyed at the study site, if applicable
- retained samples sent to a third party for bioavailability/bioequivalence, if applicable

## ***5.6    Return of investigational product***

Upon completion or termination of the study, all unused and/or partially used investigational products must be returned to ImClone Systems or a designee, if not authorized by ImClone Systems or a designee to be destroyed at the site.

## ***5.7    Investigational product retention at study site***

Opened vials may be disposed of at the investigation center as chemotherapy or biohazardous waste.

## 6 Study procedures

### 6.1 *Informed consent*

Written informed consent will be given by each patient prior to undergoing protocol-specific evaluations and prior to receiving treatment.

### 6.2 *Medical history*

Medical history will be documented at baseline. Medical history of follow-up visits may only include interim changes from last evaluation.

Concurrent medications will be documented in the patient's medical records but will not be recorded in the case report form (CRF).

### 6.3 *Physical examination*

Evaluation by pertinent body system, height (pretreatment only), weight, and body surface area (BSA), as well as ECOG performance status (pretreatment only) should be documented.

### 6.4 *Vital signs*

Vital signs will be recorded and should include temperature, pulse rate, and blood pressure.

### 6.5 *Clinical laboratory tests*

The blood-based clinical laboratory tests will include:

- Hematology profile: complete blood count with differential and platelet count
- Chemistry profile: fasting glucose, creatinine, aspartate aminotransferase (AST), alanine aminotransferase (ALT), lactate dehydrogenase (LDH), alkaline phosphatase, total bilirubin, sodium, potassium, carbon dioxide, magnesium, and amylase
- Pregnancy test: serum or urine pregnancy test

- Additional tests: 26 mL of blood will be collected and stored for additional studies of interest, including (but not restricted to) fasting insulin, fasting peptide C, triglycerides, fasting free-fatty acids and evaluation of blood-based biomarkers (refer to section 6.9.3). Briefly, blood will be collected using one EDTA (10 mL) tube and two 9-mL CPT tubes for blood cells separation and storage. Samples will be forwarded to the core laboratory to be processed within one hour of collection. Blood will be centrifuged in a standard clinical centrifuge at 2500 RPM at 4 °C for 10 minutes. Aliquots of 2.0-2.5 mL of serum should then be transferred into 2 (two) cryovials, labeled with the protocol number and the patient's unique study identification number. Cryovials will be stored at -80 °C. Peripheral blood cells will also be stored at -80 °C.

## **6.6 *Baseline tissue specimens***

Baseline tumor tissue specimens will be obtained before initiation of the investigational treatment and will be used for confirmation of diagnosis and adequacy for evaluation of biomarkers. Archival paraffin-embedded tissue may be used as the baseline specimen, provided no anti-neoplastic therapy has been administered to the patient from the time of the biopsy to study entry, in which case a new biopsy should be obtained. In the event the baseline tissue has been considered inappropriate for biomarker evaluation, a new baseline biopsy should also be obtained. Additional baseline biopsies may be performed if considered necessary by the investigator. For the purpose of this study, these additional baseline tumor biopsies will consist of an outpatient core biopsy, or a punch-biopsy performed under local anesthesia with a minimum of 4-5 mm diameter (which allows for the preparation of at least 30 slides). These specimens should be fixed in 10% formalin, preferably immediately and not more than 1 (one) hour after excision. Fixed biopsy samples will be processed for paraffin-embedding according to the Institutional Standard Operating Procedures. The paraffin blocks and slides should be labeled with the protocol number and the patient's unique study identification number and stored at room temperature. A portion of the specimen obtained may also be embedded in optimal cutting temperature compound immediately after received and not more than 1 (one) hour after excision, frozen, and stored at -80 °C for future biomarker analysis. All samples

stored at -80 °C should be placed in appropriate containers, labeled with the protocol number and the patient's unique study identification number.

## **6.7 *Imaging studies***

Computerized tomography scans or magnetic resonance imaging of the head and neck will be obtained within 30 days before treatment initiation and will be repeated in the period between the last dose of the study drug(s) and the surgical procedure to assess objective response to treatment.

## **6.8 *Audiometry***

Patients randomized to receive treatment with IMC-A12 (i.e. Arm B and Arm C) are required to have an audiometric evaluation within 90 days before starting treatment with the study drug(s). For all patients who received at least 1 dose of IMC-A12, a repeat audiometric evaluation will be performed within 90 days after surgery.

## **6.9 *Surgical procedure and post-treatment tissue specimens***

The extent of surgical resection of the tumor should be performed as originally planned by the attending physician and should not take into account response to the investigational treatment. The type of surgery will be recorded in the Operative Note (OP) and/or Procedure Note (PR) of the patient's medical record..

The surgically resected tumor specimen will be evaluated for efficacy endpoints as described in section 6.10. During surgery, an optional specimen of adipose tissue and skeletal muscle tissue from the surgical field will also be collected for post-treatment biomarker evaluation, if the patient has previously given consent and if the collection of these additional tissues is considered feasible (i.e., not associated with unreasonable risks) by the surgeon during the operative procedure. Surgery should not be extended for collection of skeletal muscle and adipose tissue. The recommended procedure for obtaining the tissue specimens is as follows: the primary tumor should be identified on

exam under anesthesia and at least 2 (two) large-cup forceps biopsies obtained prior to ligation of the tumor vessels, to avoid ischemia-induced activation of phosphatases. A portion of the tissue will be fixed in 10% formalin immediately after received and not more than 1 (one) hour after excision. Fixed biopsy samples will be processed for paraffin-embedding according to the Institutional Standard Operating Procedures. The paraffin blocks and slides should be labeled with the protocol number and the patient's unique study identification number and stored at room temperature. Another portion of the tumor specimen (preferably one sample  $\geq 2 \text{ mm}^3$  or 100 mg) will be embedded in optimal cutting temperature compound immediately after received and not more than 1 (one) hour after excision, frozen and stored at  $-80^{\circ}\text{C}$  for future biomarker analysis. Skeletal muscle and adipose tissue (preferably two or more samples  $\geq 2 \text{ mm}^3$  or 100 mg) may be obtained at the time of surgery (preferably prior to vessel ligation) or separated from the en block resected specimen containing the tumor in the pathology laboratory. A portion will be formalin-fixed (not more than 1 (one) hour after excision) and processed for paraffin-embedding according to the Institutional Standard Operating Procedures, while another portion will be embedded in optimal cutting temperature compound (not more than 1 (one) hour after excision), frozen and stored at  $-80^{\circ}\text{C}$  for future biomarker analysis. The remaining specimens resected during surgery (including the tumor, skeletal muscle and adipose tissue) and not used for routine histopathological diagnosis will also be stored for future biomarker studies.

## **6.10 *Pharmacodynamic assessments***

### **6.10.1 *Biomarker evaluation in tumor specimens***

Both baseline and post-treatment tumor specimens will be evaluated for modulation of biomarkers which could potentially indicate the molecular activity of the investigational treatments, or which could represent predictive markers of activity of such treatments. These will include:

phospho-Akt: modulation of phospho-Akt constitutes the primary endpoint of the trial.

Phospho-Akt levels should be determined in paraffin-embedded tissues by immunohistochemistry both at baseline and in the post-treatment surgical specimens. A

scoring system based on staining intensity x extension will be used to quantify the phospho-Akt levels. Staining intensity will be graded as undetectable (0), weak (1), medium (2), or strong (3). Staining extension will be graded as percentage of positive cells per square at x20 magnification. The final score will therefore range from 0 to 300.

additional biomarkers: additional biomarkers in paraffin-embedded tumor specimens at baseline and after treatment will be evaluated depending on the availability of adequate amounts of tissues for such studies. The modulation of these biomarkers by the investigational treatments and their correlation with activity of the drugs will be analyzed in an exploratory fashion. The biomarkers proposed to be studied include (but are not restricted to): IGF-1R, phospho-IGF-1R, IGF-2R, IGF-1, IGF-2, IGFBP-3, EGFR, phospho-EGFR, survivin, Ki-67, caspase-3, HIF-1 alpha, CD31, MMP-2, MMP-9, phosphorylation status of multiple kinases (using antibody arrays), micro-RNA and messenger-RNA expression levels (using high-throughput microarray chips), high-throughput proteomic analysis, genomic analysis and other biomarkers that may emerge to be important related to the use of EGFR and/or IGF-1R-targeted therapy. Investigators evaluating the endpoints involving pharmacodynamic markers (e.g., phospho-Akt) will be blinded to the clinical data of the patients, as well as treatment received.

#### **6.10.2 Biomarker evaluation in adipose tissue and skeletal muscle**

Because the most common and clinically relevant toxicity of IGF-1R inhibitors identified so far is hyperglycemia, the characterization of the molecular effects of IMC-A12 in key organs of intermediary metabolism may help elucidate the pathophysiology of impaired glucose handling in these patients, leading to the development of the most appropriate strategies for treatment of this adverse effect. Therefore, skeletal muscle and adipose tissue specimens obtained during resection of the HNSCC (i.e., after exposure to the investigational treatments) will be evaluated for the following biomarkers related to glucose metabolism (depending on the availability of adequate amounts of tissues for

such studies): insulin receptor, phosphorylated insulin receptor (phospho-tyrosine and phospho-serine) and its downstream effectors, insulin receptor substrate-1 (phospho-tyrosine and phospho-serine), glucose transporter-1, glucose transporter-4, hexokinase, PPAR-alpha, PPAR-gamma, phosphorylation status of multiple kinases (using antibody arrays), micro-RNA and messenger-RNA expression levels (using high-throughput microarray chips), high-throughput proteomic analysis, genomic analysis and other biomarkers that may emerge to be important for anti-IGF-1R therapy-induced toxicity. Correlation of these biomarkers with activity and toxicity of the study drugs will be analyzed in an exploratory fashion.

#### **6.10.3 Blood-based biomarkers**

Blood will be obtained at baseline, before the second treatment with the study drug(s), before surgical resection, and within 30 days after surgery, preferably in the morning, after at least 12 hours of fasting. The blood samples will be stored for the evaluation of biomarkers indicative of, or predictive of activity and / or toxicity of the investigational agents. These may include (but are not restricted to): free and total IGF-1 and IGF-2, IGFBP-3, insulin, peptide C, free fatty acids, triglycerides, fructosamine, a panel of 59 cytokine and angiogenic factors measured by available luminex multiplex beads kits (Bio-Plex 27-Plex & 23-Plex Kits [Bio-Rad, Hercules, CA] and Human CVD Biomarker Panel 1 kit [Linco Research, Inc., St. Charles, MOsa]), VEGF, solubleVEGFR-1, soluble VEGFR-2, osteopontin, high-throughput proteomic analysis, genomic analysis and other biomarkers that may emerge to be important for characterization of cetuximab and/or IMC-A12 activity and/or toxicity. Correlation of these biomarkers with efficacy and toxicity outcomes will be analyzed in an exploratory fashion.

### **7 Required evaluations**

#### **7.1 Pre-treatment evaluations**

Pre-treatment evaluation will include screening (to determine patient eligibility), medical history, physical examination, vital signs, clinical laboratory tests, imaging studies as described in sections 6.2, 6.3, 6.4, 6.5 and 6.7, audiometric evaluation (as described in

section 6.8), as well as adverse events assessment (as described in section 8). These should be completed no later than 30 days prior to administration of the first dose of treatment. Additionally, a baseline tumor tissue specimen should be obtained as described in section 6.6.

Results of pre-treatment evaluations must be reviewed by the principal investigator or his/her designee to ensure that all eligibility criteria have been satisfied prior to patient randomization. Written informed consent must be obtained prior to any study-specific screening evaluations and prior to receiving treatment.

## **7.2 *Treatment period***

Medical history, physical examination, vital signs, clinical laboratory tests, and imaging studies (as described in sections 6.2, 6.3, 6.4, 6.5, and 6.7), as well as adverse events assessment (as described in section 8) will be obtained within 5 days prior to the second treatment.

## **7.3 *End of therapy***

Vital signs and clinical laboratory tests (as described in sections 6.4 and 6.5) should be obtained preferably on the day of surgery, or within 2 days before surgery.

## **7.4 *Follow-up***

One post-operative evaluation should be completed within 30 days after surgery. At this time, a medical history, physical examination, vital signs (as described in sections 6.2, 6.3, 6.4), adverse events assessment (as described in section 8), and optional blood-based biomarkers (as described in section 6.5) should be obtained. Alternatively, a telephone call to assess adverse events may substitute for a medical history, physical examination, and vital signs in the event the patient is not evaluated by the investigator or his/her designee within 30 days after surgery. Audiometric evaluation should be obtained within 90 days after surgery in all patients who received at least one dose of IMC-A12 (as described in section 6.8). If toxicities related to the investigational drugs have not been resolved at the time of the post-operative evaluation, regular follow-ups are strongly

enforced with frequency to be determined by the investigator. After the end of therapy, patients should continue to be assessed by their primary physicians for long-term follow-up. Data on progression-free survival, and possible long-term toxicities will be retrospectively obtained through chart reviews. Patients (or their family members) might also be contacted (during clinic visits, by telephone, in writing, or electronic mail) to confirm or provide information on long-term follow-up.

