#### Exclusion criteria

1. Patients receiving any other agent (investigational or not) with potential anti-neoplastic activity within 3 weeks prior to obtaining the baseline tumor specimen for biomarker evaluation.
2. Patients receiving concomitant radiation
3. Prior treatment with an agent targeted at the insulin-like growth factor-1 receptor
4. History of allergic reactions attributed to compounds of chemical and biological composition similar to those of cetuximab or IMC-A12
5. Pregnant patients, or patients who are breast feeding (patients who have a positive pregnancy test within the first 30 days before the first dose of treatment are excluded)
6. Patients with uncontrolled illnesses which, in the opinion of the investigator,

could be aggravated by the administration of the study drug(s)

**Intervention and Mode of Delivery:** Following randomization, the patients will receive weekly cetuximab, weekly IMC-A12, or weekly cetuximab followed by IMC-A12 at the following doses:

Cetuximab: 400 mg/m^2 i.v. on week 1, and 250 mg/m^2 i.v. on week 2 and 3 (if applicable)

IMC-A12: 6 mg/kg/week i.v. on weeks 1, 2 and 3 (if applicable)

**Duration of Intervention and Evaluation:** Patients will receive the investigational treatment(s) for 2 doses pre-operatively, followed by surgical resection. A third dose may be given in case surgery is delayed. Only patients who had surgery within 10 days of the last treatment will be evaluable for the primary endpoint. A 30 day post-operative follow-up visit or telephone call is planned for assessment of toxicity, in addition to the regular follow-up visits in the surgical clinic. Objective response to treatment will be determined by comparing baseline imaging studies to scans obtained between the last dose of treatment and surgery.

**Primary Endpoints/Criteria for Evaluation:** The primary endpoint of this study consists of the modulation of phospho-Akt in the post-treatment, surgical tumor specimen as compared to the baseline tumor specimen in the different treatment groups. An IHC scoring system will be used to quantify phospho-Akt levels based on staining intensity x extension. Staining intensity will be graded as undetectable (0), weak (1), medium (2), or strong (3). Staining extension will be graded as percentage of positive cells per high power field at x20 magnification. The final score will therefore range from 0 to 300.

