## 8 Adverse events assessment

### 8.1 *Performing adverse events assessments*

The assessment of reported adverse events will be performed at least within 5 days before the second and, if applicable, third treatment course, and within 30 days after surgery. Adverse events will be classified according to the National Cancer Institute (NCI) Common Terminology Criteria for Adverse Events (CTCAE) version 3.0.

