### 8.3 *Adverse events definition*

#### 8.3.1 *Adverse event*

An *Adverse Event (AE)* is defined as any new untoward medical occurrence or worsening of a pre-existing medical condition in a patient administered a medicinal product that does not necessarily have a causal relationship with this treatment. An AE can therefore be any unfavorable and unintended sign (including an abnormal laboratory

finding, for example), symptom, or disease temporally associated with the use of a medicinal (investigational or marketed) product, whether or not considered related to the medicinal (investigational or marketed) product. Planned medical interventions (e.g., planned surgical resection) will not be considered an adverse event. For the purpose of this study, adverse events that in the opinion of the treating investigator are related to planned surgical procedure (e.g., usual pain, usual bleeding, intra- or post-operative electrolyte imbalances and other clinically insignificant laboratory abnormalities) will not be captured and/or reported.

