- **All life-threatening or fatal events**, that are unexpected, and related to the study drug, must have a written report submitted within **24 hours** (next working day) of knowledge of the event to the Safety Project Manager in the IND Office.
- The MDACC "Internal SAE Report Form for Prompt Reporting" will be used for reporting to the IND Office.
- Serious adverse events will be captured from the time the patient signs consent until 30 days after the last dose of drug. Serious adverse events must be followed until clinical recovery is complete and laboratory tests have returned to baseline, progression of the event has stabilized, or there has been acceptable resolution of the event.
- Additionally, any serious adverse events that occur after the 30 day time period that are related to the study treatment must be reported to the IND Office. This may include the development of a secondary malignancy.

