## **8.5 *Collection of safety information***

Pre-existing toxicities will be collected and noted on patient's medical record.

Additionally, collection of AE information will be performed from the time the patient receives the initial infusion of the study drug(s), and must continue throughout the study until 30 days after the last dose, unless specified otherwise in the protocol. This includes pre-existing conditions or symptoms that worsened during the study, or whose relationship to the investigational product changed, but does not include pre-planned hospitalizations or procedures for pre-existing conditions. In addition, the investigator should notify Eli Lilly & Co. of any SAE or outcome that may occur after this time period that he/she believes to be related to IMC-A12 and/or cetuximab. An AE report must contain the following four basic elements: (1) an identifiable patient; (2) a suspect medicinal product; (3) an identifiable reporting source; and (4) an identifiable event or outcome. All identified AEs must be recorded and described in patient's medical record. If known, the diagnosis of the underlying illness or disorder should be recorded in

addition to the presenting symptoms. The following information should be captured for all AEs: the date of the onset and resolution; the severity of the event as determined by PI or study collaborator (see definitions in NCI-CTCAE, Version 3.0); the investigator's opinion of the relationship of the event to the investigational drug/s (certainly/definitely, probably, possibly, unlikely, or not related); the treatment required for the AE; information regarding resolution/outcome; and if the AE is serious, a clear identification of the seriousness outcome.

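### Scheduled adverse event inquiry around surgery is weak and uneven, although the collection window covers last dose to surgery and most of the post-operative month

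*Combined protocol and SAP*

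**What the plan says.** **Scheduled assessments.** Section 8.1 requires adverse event assessment "at least within 5 days before the second and, if applicable, third treatment course, and within 30 days after surgery". The study events table (7.5) agrees: its adverse event row is marked for pre-treatment, treatment period and follow-up, and the End of Therapy cell is empty. Section 7.3 lists only vital signs and laboratory tests for that visit.

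**Post-operative contact.** Section 7.4: "One post-operative evaluation should be completed within 30 days after surgery". A telephone call may replace the examination. The synopsis (Duration of Intervention and Evaluation) puts it differently: "A 30 day post-operative follow-up visit or telephone call is planned for assessment of toxicity".

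**Collection window.** Under 8.5, collection starts at the first infusion and "must continue throughout the study until 30 days after the last dose, unless specified otherwise in the protocol". For serious events, 8.3.2 says "Serious adverse events will be captured from the time the patient signs consent until 30 days after the last dose of drug". Beyond that, 8.3.2 adds that "any serious adverse events that occur after the 30 day time period that are related to the study treatment must be reported", and 8.5 asks the investigator to notify the supporting company of later serious events or outcomes believed related to either drug.

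**Surgical events.** Under 8.3.1, adverse events that the treating investigator relates to the planned operation "will not be captured and/or reported". Section 8.3.2 exempts such events from serious event reporting to the IRB. It still sends serious events to the IND Office whatever their attribution, unless the protocol states otherwise.

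**The concern.** Safety, particularly before surgery, is the first secondary objective (2.2). Section 9.2.3 says that IMC-A12 has no earlier pre-operative experience. It promises close monitoring, and reconsideration of the study if peri-operative complications exceed expectation, but gives no schedule. A complication rate can be judged or compared between arms only if patients are asked at comparable times.

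The schedule works against this in two ways. First, nobody is required to ask about the final dose until after the operation. By then drug and surgical effects are hard to separate, and the attribution that decides whether an event is recorded is made in an open-label study (4.1). Electrolytes show the difficulty: 9.1.5 reports hypomagnesemia in about half of cetuximab patients (severe in 10-15%), while 8.3.1 gives electrolyte disturbance during or after surgery as an example of an event not to be captured. Second, one patient may be asked once in the first post-operative week and another on day 30, so the period covered by scheduled inquiry differs between patients.

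**Working it through.** The plan gives no figure of its own to reproduce. The check is date arithmetic on its rules.

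**Inputs.** Surgery is day 0 and the last dose is on day -g.
- g = 2: planned second dose (4.1).
- g = 5: early end of the second-dose window, 2 + 3 (4.1).
- g = 10: evaluability limit (12.3).
- Adverse event check 0 to 5 days before the last dose (7.5, 8.1).
- Post-operative contact on any day c up to 30 (7.4). c = 7 is taken as an illustration.

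**Formulas.**
- Collection ends on post-operative day E = 30 - g.
- Days before post-operative day 30 that fall outside routine collection: 30 - E = g.
- Collection window left after the contact: E - c.
- Interval between scheduled checks if the contact is on day 30: (0 to 5) + g + 30.

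| Last dose | Collection ends (post-op day) | Days outside, to day 30 | Window left after a day-7 contact | Interval between checks, contact on day 30 |
|---|---|---|---|---|
| day -2 | 30 - 2 = 28 | 2 | 28 - 7 = 21 | 32 to 37 days |
| day -5 | 30 - 5 = 25 | 5 | 25 - 7 = 18 | 35 to 40 days |
| day -10 | 30 - 10 = 20 | 10 | 20 - 7 = 13 | 40 to 45 days |

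An early contact leaves a stretch of the window with no later scheduled inquiry. A late one leaves about a month or more, with surgery inside it, between two checks.

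The 10-day limit defines only the population for the primary endpoint. The safety population takes anyone dosed, and 4.1 lets surgery be postponed, so collection could end before post-operative day 20 for some patients.

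**Does the exception clause in 8.5 move the end date?** Sections 7.4, 7.5 and 8.1 say when an assessment takes place. None says that collection runs until then. The sentence setting the serious event window in 8.3.2 carries no such exception. For non-serious events the end date is ambiguous at best; for serious events it is tied to the last dose.

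**The case against.** A reader might infer that the plan fails to observe the peri-operative period. It does not: the collection window covers the whole interval from last dose to surgery, and post-operative days 0 to 28 as planned or 0 to 20 at the evaluability limit.

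A reader might also infer that a day-7 contact leaves 23 of 30 post-operative days (30 - 7) unobserved. That fails too. The synopsis places the contact on top of routine surgical clinic visits, and serious event capture does not depend on it. What is absent is a further scheduled study inquiry, and within the collection window that is 21 or 13 days.

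Nor is there nothing between last dose and surgery. Vital signs, blood counts and chemistry, including fasting glucose and magnesium (6.5), are taken, and imaging is done. Section 9 calls for continuous monitoring and tells patients to telephone between visits. Section 8.1 sets a minimum. Section 7.4 adds follow-up of unresolved related toxicity and later chart review.

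These provisions reduce the gap without closing it. Continuous monitoring applies while patients are on study therapy, and whether that extends past the last dose is undefined. Calling in depends on the patient. Under 8.9, an abnormal laboratory value enters the adverse event record only if it leads to withdrawal, needs intervention or has medically important manifestations. Reporting after the window covers only events judged treatment-related.

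Two further objections have force. A dose-based end date gives every patient the same time after dosing and is a legitimate choice. The synopsis and 7.4 can be read together, since a day-30 contact meets both; but a day-7 contact meets only 7.4.

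**Conclusion.** The point holds as one about scheduled ascertainment. Three features stand: no adverse event assessment is scheduled between last dose and surgery; the single post-operative contact has no earliest day and is described differently in the synopsis; and routine collection ends 2 to 10 days before post-operative day 30 for last doses on day -2 to day -10.

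A plan followed exactly can therefore yield uneven peri-operative data for the first secondary objective and for the commitment in 9.2.3. The primary endpoint is untouched. The documents do not show that any particular event would escape reporting. The figures rest on last-dose intervals taken from 4.1 and 12.3 and on an illustrative day-7 contact. Worth changing, because it bears on safety and costs little.

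**What to change.** 1. Mark an adverse event assessment in the End of Therapy column of 7.5, and add it to 7.3 and 8.1. It should take place after the last dose and before surgery, at the visit that already exists.
2. Set the follow-up adverse event contact at or just after post-operative day 30, by visit or the telephone call already allowed, and align 7.4, 7.5, 8.1 and the synopsis.
3. In 8.5 and 8.3.2, end adverse event and serious adverse event collection 30 days after surgery, or 30 days after the last dose if there is no surgery. Keep the provisions for later related events.

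**Cost.** The changes are wording, one added inquiry at an existing visit, and at most one call for a patient whose post-operative visit falls earlier. Time since last dose at the end of collection would vary: 30 + 2 = 32 days for day -2 and 30 + 10 = 40 for day -10. A tabulation cut at 30 days after the last dose can be reported alongside, so that comparison is kept.

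**Limit.** The exclusions for surgery-attributed events in 8.3.1 and 8.3.2 remain. The change does separate toxicity present before the operation from what appears after it.
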